5.2. Treatment Assignment

A unique 4-digit patient number will be assigned to each patient when the patient signs the informed consent form (ICF).

Patients will be assigned to dulaglutide 1.5 mg, placebo, or 1 of 4 LY3298176 dose levels. Patients who meet all criteria for enrollment will be randomized at Visit 3 and assigned to their respective treatment arms via interactive web response system (IWRS) using the following stratification variables: baseline HbA1c (<8.5%, $\ge8.5\%$), metformin use (Yes, No), and BMI (<30, ≥30). There will be equal randomization to the treatment arms (1:1:1:1:1). However, LY3298176 placebo patients will be randomized such that a portion will be randomized to each cohort in order to receive the same dose volume as that cohort in order to maintain the study blind. For the active dulaglutide 1.5 mg group, LY3298176 placebo patients will be distributed through the treatment groups in order to maintain the blind.

The randomization scheme will be performed using IWRS that will ensure balance between treatment arms.

5.3. Determination of Sample Size

Approximately 300 patients will be randomized to placebo, dulaglutide, or 1 of the 4 LY3298176 treatment arms assuming a 10% dropout rate resulting in approximately 45 completers per arm.

The Bayesian approach using a dose-response model with respect to an HbA1c change from baseline to 26 weeks will provide approximately 98% probability to show with 90% confidence that at least 1 LY3298176 dose has superior glycemic control over placebo with a superiority bound of -0.8%. The sample size also provides >95% probability to show with 80% confidence that at least 1 LY3298176 dose has non-inferior glycemic control compared with dulaglutide from baseline to 26 weeks with a 0.3% non-inferiority bound. This assumes a profile for the change in HbA1c from baseline to 26 weeks shown in Table 5.1, and a standard deviation (SD) of 1.0%.

In addition, this sample size also provides approximately 89% probability to show with 60% confidence that at least 1 LY3298176 dose has superior weight loss compared with dulaglutide from baseline to 26 weeks with a superiority bound of -2 kg. This assumes a profile for the change in body weight from baseline to 26 weeks shown in Table 5.1, and an SD of 6 kg.

Table 5.1. Dose-Response Assumption Used in Sample Size Determination

	Placebo	LY 1	LY 5	LY 10	LY 15	Dulaglutide
CFBL HbA1c (%)	0%	-0.74%	-1.17%	-1.29%	-1.44%	-1.28%
CFBL Body Weight (kg)	0	-2.0	-3.0	-5.0	-6.0	-2.5

Abbreviations: CFBL = change from baseline; HbA1c = hemoglobin A1c; LY = study drug LY3298176.

6. A Priori Statistical Methods

6.1. General Considerations

Statistical analysis of this study will be the responsibility of Lilly or its designee. Any change to the statistical methods described in the protocol will require an amendment only if it changes a principal feature of the protocol. Any other change to the statistical analyses and the justification for the change will be documented in the clinical study report. Additional exploratory analyses of data may be conducted as deemed appropriate without further changes made to the protocol or SAP even after the database lock (DBL).

Tests of treatment effects will be conducted at a one-sided alpha level of 0.1 and/or one-sided 90% credible interval (CI) for the Bayesian dose response analysis, and at a two-sided alpha level of 0.05 for other analyses, unless otherwise stated. No adjustments for multiplicity will be performed.

The baseline visit will be Visit 3. The baseline values used for the analyses will be the last scheduled baseline value obtained for each patient prior to first dosing. For all variables, if baseline data are not available or if they are missing, then the last non-missing measurement taken prior to first treatment will be used for the baseline measurement.

All efficacy and safety data will be summarized by each treatment group at each scheduled visit unless otherwise indicated. A scheduled visit is based on the actual visit number reported by the site. Imputed data may be applied in model-based data analysis, but will not be used in data listing.

6.1.1. Analysis of Repeated Measures

The mixed model for repeated measures (MMRM) using restricted maximum likelihood (REML) will be used to fit change from baseline values at all scheduled visits. The model will include the treatment group, strata (that is, baseline HbA1c category, baseline BMI category, and metformin use [yes, no]), visit, and treatment-by-visit interaction as fixed effects, baseline value of the dependent variable as a covariate, and patient as a random effect. If the analysis is on the primary endpoint, baseline HbA1c category will not be included in the model in addition to the continuous covariate of baseline HbA1c. To model the covariance structure within patients, the unstructured covariance matrix will be selected initially. If the unstructured covariance structure leads to nonconvergence, the following covariance structures will be tested in order:

- toeplitz with heterogeneity
- autoregressive with heterogeneity
- compound symmetry with heterogeneous variances
- toeplitz
- autoregressive
- compound symmetry without heterogeneous variances
- compound symmetry

The first covariance structure that converges will be used.

Kenward-Roger method will be used to estimate the denominator degrees of freedom and the restricted maximum likelihood approach will be used to determine the model estimates.

The MMRM model will present least squares (LS) mean estimates for each scheduled week by treatment group and 2-sided 95% CIs for mean changes from baseline within and (when warranted) between treatments. T-statistics corresponding to the Type III sums of squares for the differences in the LS means will be used to obtain p-values for treatment group comparisons.

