- d is the dose arm index, with d = 0,...,D (d=0 as placebo, and d=D as dulaglutide)
- D is the number of non-placebo dose arms, including dulaglutide. D is also the dose arm index for dulaglutide.
- x_{dT} is the dose strength, with d = 0, 1, ..., D-1 in ascending order. Dulaglutide is not included in the Hierarchical Logistic model, and therefore does not require a dose strength.
- Λ_i and λ_i are, respectively, the prior means and variances of a_i , i = 1,2,3.
- θ_{dT} is the modeled dose arm effect at dose d at the final time point T of the 26-week of the study.
- E (1/a₄) = 1/Λ_μ and Λ_n represents the weight of the prior information carried in Λ_μ.
 E (1/σ²) = 1/σ_μ and σ_n represents the weight of prior information carried in σ_μ².

The dose strength, x_{dT} , used in the model will reflect the actual selected doses for the study. The planned values for x_{dT} are shown in Table 6.2. Dulaglutide is modeled separately. The magnitude of the parameters x_{dT} impact the estimation in the dose-response model.

Dose Strength Parameter	Dose Strength (mg)
x_0	0*
x_1	1
x_2	5
x_3	10
x_4	15
x_5	NA

Table 6.2. Dose Strength Parameters and Corresponding Dose Strengths

Abbreviation: NA = not applicable.

Any missing responses for the primary outcome will be imputed using the longitudinal integrated two-component prediction (ITP) model. This is a slight deviation from the protocol, which is specified to use the Simple Linear Regression (SLR) model. The model is as follows:

$$Y_{djt} = (\omega_d + S_{dj} + \varepsilon_{djt}) \times (\frac{1 - e^{k_d t}}{1 - e^{k_d \times 26}}) = f(d, t) + (S_{dj} + \varepsilon_{djt}) \times (\frac{1 - e^{k_d t}}{1 - e^{k_d \times 26}})$$

Where Y_{djt} represents the response for dose d, subject j at time t. where time is t = 1, 2, ..., 9 (1, 2, 4, 8, 12, 16, 20, 24, 26 weeks), T is the 26 week time point, patient is $i = 1, ..., N_d$, where N_d is the number of patients for dose d, and d = 0, ..., D. f(d,t) represents the mean response.

The prior distributions for time t and d = 0, ..., D dose levels are as follows:

$$\begin{cases} \omega_{d} \sim N(\omega_{\mu}, \omega_{\sigma}^{2}) = N(0,3^{2}), \\ S_{dj} \sim N(0, \tau^{2}), \\ \varepsilon_{djt} \sim N(0, \lambda^{2}), \\ \lambda^{2} \sim IG\left(\frac{\lambda_{n}}{2}, \frac{\lambda_{\mu}^{2} \lambda_{n}}{2}\right), \\ \tau^{2} \sim IG\left(\frac{\tau_{n}}{2}, \frac{\tau_{\mu}^{2} \tau_{n}}{2}\right), \\ k \sim N(\mu_{k}, \sigma_{k}^{2}), \end{cases}$$

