6.9.2.2. Continuous Variable Analyses

The MMRM model described in Section 6.1.1 will be performed on the following variables to obtain inference for the corresponding secondary objectives:

- Body weight change from baseline
- Change from baseline of HbA1c

- Change from baseline of FBG
- Change from baseline of waist circumference

BMI (kg/m²) will be calculated at each visit at which weight is measured, using height as measured during screening. Change from baseline in BMI will be listed and summarized.

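### The MMRM in SAP 6.1.1 has no baseline-by-visit term, so HbA1c (and, less so, body weight) loses most of its baseline covariate adjustment at Week 26, at a modest cost in precision

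*SAP*

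**What the plan says.** SAP 6.1.1 defines the MMRM. It "will be used to fit change from baseline values at all scheduled visits", with treatment, strata, "visit, and treatment-by-visit interaction as fixed effects", and the "baseline value of the dependent variable as a covariate, and patient as a random effect". For the within-patient covariance, "the unstructured covariance matrix will be selected initially". No baseline-by-visit term is listed. The protocol's MMRM (10.3.3.2) has none either; its robustness checks cover treatment-by-strata and treatment-by-baseline interactions only.

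The model is widely used. SAP 6.9.2.2 states: "The MMRM model described in Section 6.1.1 will be performed on the following variables to obtain inference for the corresponding secondary objectives"; the list is weight, HbA1c, fasting glucose and waist. SAP 6.9.1.3 uses it on three analysis sets as a supportive analysis of the primary outcome. SAP 6.14.2 names it for HbA1c and weight at the second interim analysis. Several safety, patient-reported and biomarker sections refer to it as well. Its tests are run "and at a two-sided alpha level of 0.05 for other analyses, unless otherwise stated" (SAP 6.1). HbA1c is measured at "1, 2, 4, 8, 12, 16, 20, 24, 26 weeks".

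**The concern.** At Week 1 the HbA1c change is small and can depend only slightly on where the patient started. By Week 26 the dependence may be substantial. A single slope has to compromise between visits. Under an unstructured covariance, generalized least squares weights that compromise towards the visits with the least residual variance, which are the early ones. The fitted slope is then close to the Week-1 slope, and the covariate does little at the visit of interest.

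What is at stake is precision. For HbA1c, SAP 6.1.1 drops the baseline HbA1c category because continuous baseline HbA1c is in the model. If that covariate has almost no effect at Week 26, the intended adjustment for a stratification factor is largely absent there. The same holds at Week 12, the visit that the second interim analysis reaches in support of preliminary Phase 3 dose selection.

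**Working it through.** **Plan's own figure.** The documents give no precision or power figure for the MMRM. The nearest is the probability of about 98% for at least one dose beating placebo by 0.8% on HbA1c (SAP 5.3). With SD 1.0% and 45 completers per arm, SE = 1.0 × √(2/45) = 0.211. For LY 15 mg alone, (1.44 − 0.80)/0.211 − 1.282 = 1.75, giving 96.0%. Simulating all four doses against a shared placebo arm gives 98.3%. The stated figure is reproduced from the unadjusted SD, so it takes no credit for a baseline covariate.

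**Inputs from the documents.** Nine HbA1c visits; SD of change 1.0% for HbA1c and 6 kg for weight; 50 randomized per arm with 10% dropout; prior mean k = −0.1 per week for the time course (SAP 6.9.1.1).

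**Assumptions not in the documents.** Correlation R between baseline and Week-26 change: 0.30 to 0.60 for HbA1c, 0.1 to 0.4 for weight. Baseline SD: HbA1c 0.9%, weight 18 kg, fasting glucose 50 mg/dL. Within-patient residual correlation 0.4 to 0.8. Measurement SD: HbA1c 0.1% to 0.3%, weight 0.7 to 1.5 kg. The baseline slope is taken to grow with the time course.

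**Formulas.** Let β be the vector of true visit-specific baseline slopes, S the residual covariance and **1** a vector of ones.
- Time course: f(t) = (1 − e^(−0.1t)) / (1 − e^(−2.6)). This is 0.10 at Week 1, 0.36 at Week 4, 0.755 at Week 12 and 1 at Week 26.
- Common slope in large samples: b = **1**′S⁻¹β / **1**′S⁻¹**1**.
- SE ratio at a visit, planned model against one with baseline-by-visit: √(1 + (β_visit − b)² × SD_base² / residual variance).
- Ceiling, with no covariate at all: 1/√(1 − R²).

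**Worked case, HbA1c, R = 0.45, measurement SD 0.2%, residual correlation 0.65.**
- Week-26 slope = −0.45/0.9 = −0.50. The common slope comes out at −0.04, about 8% of it.
- Week 26: residual variance = 1 − 0.45² = 0.7975. Ratio = √(1 + 0.46² × 0.81/0.7975) = 1.10.
- Week 12: slope = −0.50 × 0.755 = −0.377. Residual variance = (0.7975 − 0.04) × 0.755² + 0.04 = 0.472. Ratio = √(1 + 0.337² × 0.81/0.472) = 1.09.

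**Ranges at Week 26, HbA1c.** The common slope keeps 2% to 19% of the Week-26 slope (4% to 26% with k = −0.2).

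| R | SE increase | Ceiling | Effective sample size |
|---|---|---|---|
| 0.30 | 3–5% | 5% | 91–94% |
| 0.45 | 7–11% | 12% | 81–87% |
| 0.60 | 14–24% | 25% | 65–77% |

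**Check by fitting.** Both unstructured models, without strata terms, were fitted to simulated trials (6 × 50 patients, 10% dropout, 120 replicates per setting). With simple randomization, the mean SE for LY 15 mg versus placebo fell from 0.204 to 0.196 (R = 0.30), from 0.201 to 0.184 (0.45) and from 0.197 to 0.166 (0.60) when baseline-by-visit was added. The planned model's SE is thus about 4%, 9% and 19% larger. Bias was no more than about 0.02 under either model.

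**Other endpoints.**
- Weight: the common slope keeps 3% to 8% of the Week-26 slope, but the SE rises only 0.4% to 9%. At R = 0.4, the Week-26 slope is −0.133, the common slope −0.004 and the residual variance 36 × (1 − 0.16) = 30.24; the ratio is √(1 + 0.129² × 324/30.24) = 1.086.
- Fasting glucose (Weeks 2, 4, 12, 26) with an early plateau: 84% to 100% of the slope is kept and the SE rises by at most 0.6%.
- Any endpoint with a constant baseline slope: no loss.

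**The case against.** Most of the case on the other side stands, and it limits the point.

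- A reader might infer that Week-26 comparisons lose most of their precision. They do not. The response is already change from baseline, so only the covariate's extra gain is at risk, and the ceilings above bound it.
- A reader might extend the loss to every endpoint that uses the model. Only HbA1c, weight, blood pressure and pulse have a Week-1 visit. Fasting glucose starts at Week 2, waist and lipids at Week 4, and several biomarkers at Week 12.
- A reader might conclude that chance baseline imbalance goes uncorrected. Randomization is stratified at HbA1c 8.5%. If baseline HbA1c is roughly normal, a cut 0 to 0.8 SD from the mean removes about 64% to 50% of the variance in arm-mean imbalance. Without stratification, a 1-SD imbalance is 0.9 × √(2/45) = 0.19%, which shifts the contrast by 0.19 × 0.46 = 0.09% in the worked case. With it, the shift is 0.09 × √0.36 to 0.09 × √0.50, about 0.05% to 0.06%. The reported standard error may therefore overstate the real loss; the simulated empirical standard errors are too noisy to say by how much.
- Other analyses exist. HbA1c has the primary Bayesian model and a Week-26 LOCF ANCOVA with its own slope (SAP 6.1.2, 6.9.1.3). Weight has a Bayesian dose-response analysis (SAP 6.9.2.1). Both have a multiple-imputation analysis that may use ANCOVA (SAP 6.9.2.3).
- The second interim analysis is for internal decisions and cannot stop the study for efficacy or futility.

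None of this supplies the missing term. The ANCOVA relies on carrying observations forward, the multiple-imputation analysis may itself use the MMRM, and the MMRM is the only efficacy model named for the second interim analysis.

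**Conclusion.** The point holds as a minor matter of efficiency. As specified, the MMRM loses most of the baseline covariate adjustment at Week 26 for HbA1c and weight, and at Week 12 for HbA1c. The Week-26 standard errors are about 3% to 24% larger than needed for HbA1c and at most about 9% larger for weight, with under 1% for fasting glucose that plateaus early. At R = 0.45 for HbA1c, the cost is like losing roughly 6 to 9 of 45 completers per arm (45 × 13% to 19%).

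These sizes rest on the assumed correlations, baseline SDs and residual structure, and on a time course taken from a prior mean. The direction does not depend on the exact values, provided the baseline slope grows over visits and the early visits vary least. The documents do not support reading this as bias, as a threat to the primary analysis or to the stated 98%, or as a loss common to all secondary and safety endpoints.

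**What to change.** Add a baseline-by-visit interaction to the MMRM in SAP 6.1.1, so that each visit has its own baseline slope, and let the sections that refer to 6.1.1 inherit it. For the nine HbA1c visits in the treatment period this costs 8 degrees of freedom out of about 270 completers; endpoints with fewer visits cost less. It needs no new data. It changes no principal feature, so under SAP 6.1 no protocol amendment is needed and the change can be recorded in the clinical study report. Where the slope is constant over visits, little is lost by including the term.

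Do not add strata-by-visit terms on condition that the model converges. For HbA1c, BMI category and metformin use would take a further 2 × 8 = 16 degrees of freedom, and the condition would make the model depend on the data.

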10.3.3.2. Supporting Analyses of Primary Outcome

Supportive analyses of the primary efficacy outcome for the mITT dataset will be MMRM using restricted maximum likelihood with metformin use (yes/no), treatment, visit, and treatment-by-visit interaction as fixed effects, HbA1c baseline as a covariate, and patient as a random effect. The dependent variable will be the post-baseline change from baseline values. The unstructured covariance matrix will be selected initially. If the unstructured covariance structure leads to nonconvergence, Akaike's information criterion will be used to select the best covariance structure. The treatment p-value will be used as evidence of difference between active drug and placebo, whereas the comparison of least-square (LS) means versus placebo (unadjusted for multiple comparisons) will provide magnitude and significance of this difference.

A further robustness check will be made using the PP dataset and applying the same MMRM procedure as described in the above paragraph. Any differences in conclusions will be further investigated by examining differences in the mITT and the PP datasets.

The MMRM analysis will be examined for robustness by checking for treatment-by-strata and treatment-by-baseline HbA1c interactions in the MMRM model using the mITT dataset. If any of these checks give positive indications, supportive analyses accounting for the identified issues will be compared along with the primary analysis.

An analysis of covariance (ANCOVA) model will be used for the primary efficacy outcome for the mITT dataset with fixed effects of metformin use, treatment, and baseline HbA1c as covariates. Missing endpoints will be imputed using last observation carried forward (LOCF). For this model, the endpoint is defined as latest HbA1c measurement obtained for a patient in the time interval between randomization and 26 weeks after randomization.

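### SAP 6.1.1 pairs a random patient effect with an unstructured covariance, which cannot be identified, and its fallback rule leaves Week-26 standard errors exposed to a misspecified correlation pattern

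*SAP*

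**What the plan says.** SAP 6.1.1 lists among the model terms "baseline value of the dependent variable as a covariate, and patient as a random effect". It then specifies the within-patient covariance: "To model the covariance structure within patients, the unstructured covariance matrix will be selected initially". If that fit does not converge, seven structures are tried in order. The first is "toeplitz with heterogeneity", followed by heterogeneous autoregressive, heterogeneous compound symmetry, and then homogeneous versions. The last two entries, compound symmetry without heterogeneous variances and plain compound symmetry, are the same structure. The stopping rule is "The first covariance structure that converges will be used". For inference, "Kenward-Roger method will be used to estimate the denominator degrees of freedom"; no empirical standard error is named.

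Protocol 10.3.3.2 has the same pairing of a random patient effect with an unstructured matrix, but its fallback differs: "Akaike's information criterion will be used to select the best covariance structure". The SAP's revision history (section 3) does not list this change. SAP 6.9.1.1, by contrast, openly declares its change of longitudinal model as a deviation from the protocol.

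This model supports the primary outcome (SAP 6.9.1.3). It gives the inference for body weight, HbA1c, fasting glucose and waist circumference (6.9.2.2), and it is reused for vital signs, lipids, SMBG, patient-reported outcomes and biomarkers. It is also the HbA1c and weight analysis at the second interim (6.14.2), which informs preliminary Phase 3 dose selection.

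**The concern.** A random patient effect adds one constant to every element of the within-patient covariance matrix. An unstructured matrix already contains any such constant, so the likelihood cannot separate the two. A program given both terms may report a singular Hessian or nonconvergence, and under the SAP that report alone sends the analysis down the fallback list.

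What follows is then not harmless by default. Toeplitz and first-order autoregressive structures index correlation by visit number, not by weeks. If the true correlation between neighbouring visits is low early and high late, one lag-1 parameter must serve both. The fitted variances, including the one at Week 26, can shift to compensate. Kenward-Roger adjusts for small samples but does not correct a wrong covariance structure. At stake are the Week-26 intervals and p-values for the secondary continuous endpoints, and the corresponding MMRM results seen at the second interim.

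**Working it through.** The plan gives no precision figure for this model, so there is none to reproduce. Inputs from the documents: HbA1c visits at Weeks 1, 2, 4, 8, 12, 16, 20, 24 and 26 (SAP 6.9.1.1); Week-26 SD 1.0% and about 45 completers per arm (SAP 5.3). Assumed, because the documents are silent: SDs before Week 26 and all between-visit correlations.

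**1. Identifiability.** Unstructured at 9 visits: 9 × 10 / 2 = 45 parameters. Adding the random-effect variance gives 46. For any constant c, U + vJ = (U + cJ) + (v − c)J, where J is the matrix of ones, so the rank is 45. Every split gives the same marginal covariance and hence the same standard error. With the random effect kept, homogeneous Toeplitz (10 parameters, rank 9) and compound symmetry (3, rank 2) are also redundant. Heterogeneous Toeplitz (18), heterogeneous autoregressive (11), heterogeneous compound symmetry (11) and homogeneous autoregressive (3) are full rank.

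**2. Spacing.** The gaps between successive visits are 1, 2, 4, 4, 4, 4, 4 and 2 weeks. Toeplitz and autoregressive structures give all eight the same correlation.

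**3. Effect on the Week-26 standard error.** For a true covariance V, the large-sample fit of structure S minimises log|S| + tr(S⁻¹V). With complete data and treatment-by-visit means, the Week-26 contrast is essentially a difference in raw means, so reported SE / true SE = √(S₂₆/V₂₆). Results for HbA1c, without the random effect:

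| Assumed truth | Heterogeneous Toeplitz | Heterogeneous AR |
|---|---|---|
| Response growing over time plus constant noise | 0.75–0.83 | 0.80–0.89 |
| Random intercept and slope | 0.82 | 0.81 |
| Random walk plus noise | 0.82–0.85 | 0.82–0.85 |
| SAP's ITP form, noise scaled by the growth curve, common k | 1.00 | 1.00 |
| Correlation decaying with calendar time | 1.01–1.04 | 1.03–1.04 |

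**4. One case in full.** Let g(t) = (1 − e^(−0.1t))/(1 − e^(−2.6)), using the SAP's prior mean for k, and V(s,t) = 0.95² g(s)g(t), plus 0.30² on the diagonal.
- Week 1: g = 0.103, variance 0.9025 × 0.0106 + 0.09 = 0.0995, SD 0.32.
- Week 26: variance 0.9025 + 0.09 = 0.9925, SD 1.00, matching the planning value.
- Correlation of Weeks 1 and 2: 0.16. Correlation of Weeks 24 and 26: 0.91. A single lag-1 parameter must cover both.
- Heterogeneous Toeplitz ratio: 0.77.

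If the noise is instead multiplied by g(t), as in the SAP's ITP model, the covariance is heterogeneous compound symmetry. That is a special case of heterogeneous Toeplitz, and the ratio is 1.00.

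**5. Random effect kept in the fallback.** The SAP does not say it is dropped. Heterogeneous Toeplitz with it gives 0.76–0.92 under the growing-response truths and 0.91–1.03 under the ITP, calendar-decay and constant-SD truths.

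**6. Later fallbacks.** The homogeneous structures give 0.98–1.00 if the SD is constant over time and down to 0.65 if it grows steeply.

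**7. What a ratio means.** Coverage of a nominal 95% interval is 2Φ(1.96 × ratio) − 1: 0.75 gives 85.8%, 0.83 gives 89.6%, 1.00 gives 95.0%, 1.03 gives 95.6%. In HbA1c units the true SE of a difference is 1.0 × √(2/45) = 0.211, so the half-width should be 1.96 × 0.211 = 0.413. At a ratio of 0.75 it would be reported as 0.75 × 0.413 = 0.310.

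**8. Two-visit endpoints.** Unstructured has 2 × 3 / 2 = 3 parameters; heterogeneous Toeplitz has two variances and one correlation, also 3. They are the same model, so no distortion arises from that fallback.

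**The case against.** The random patient effect may be loose wording for within-patient correlation. The next sentence but one describes how that correlation is modelled, and a programmer may simply fit the unstructured matrix alone. Harm then needs a chain: both terms coded literally, nonconvergence reported, the redundant term not removed, and an unfavourable true covariance. The documents give no likelihood for any link. This argument stands as a limit on probability, but the text does state both terms, and the fallback is what the SAP prescribes if the fit fails.

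The only covariance form the documents state for HbA1c over time, the ITP model, makes the first fallback correct when k is common to the arms. That also stands, as one end of the range. It does not exclude the other end: measurement noise that does not shrink with the early response is a plausible alternative, and it produces the shortfall.

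The change from AIC is weak ground by itself. AIC could also pick heterogeneous Toeplitz, a fixed order is less data-driven, and Protocol 10.3.1 and SAP 6.1 allow non-principal changes to be documented without an amendment. HbA1c also has ANCOVA and Bayesian analyses, and weight has a Bayesian one. All this is fair, and it makes the AIC difference a matter of record. Fasting glucose and waist circumference have no such named alternative.

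A reader might infer that the fallback's standard errors simply are 13–20% too small, or that every Week-26 comparison is affected. Neither is supported. The first turns an assumed covariance into a fact. The second overlooks patient-reported outcomes (Weeks 12 and 26) and FGF-21, adiponectin, β-hydroxybutyrate and the bone markers (Visits 11 and 16), which have two scheduled post-baseline visits.

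**Conclusion.** The point holds as a specification fault with an uncertain consequence. The over-parameterisation is certain: 46 parameters, rank 45 at nine visits. It does not itself bias any standard error; its risk is an unnecessary move to the fallback. If heterogeneous Toeplitz is then used for HbA1c, the Week-26 standard error lies between about 25% too small and slightly too large, depending on a covariance the documents do not describe. At the unfavourable end, a nominal 95% interval covers about 86%. These are large-sample HbA1c figures; no size is given here for fasting glucose, waist circumference or lipids, which have fewer visits.

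The shortfall is not confined to the homogeneous structures. A separate variance at each visit does not protect Week 26 when the correlation pattern is wrong. If the unstructured model is fitted without the random effect and converges, nothing here arises. The primary Bayesian analysis does not use this model.

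**What to change.** In SAP 6.1.1:
- Delete the random patient effect, or state that the within-patient covariance matrix represents it and that no separate random term is fitted.
- Use any fallback structure only with empirical (sandwich) standard errors and compatible degrees of freedom, for example between-within, in place of Kenward-Roger.
- Record that the ordered list replaces the protocol's AIC rule.
- Remove the duplicate compound-symmetry entry.

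The cost is SAP wording and one procedure option. If the unstructured model converges without the random effect, its Kenward-Roger inference is unchanged. The downside is limited to the fallback case: sandwich errors are slightly more variable at about 50 patients per arm, and Kenward-Roger is given up there.
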